### **3.4 POOLING OF INVESTIGATIONAL SITES**

Analysis will not be pooled as the primary and secondary analysis sufficiently account for the different centres.

For the primary and secondary analyses, the models are adjusted for site as a random effect. Sites that have less than 5 participants will be grouped into an ‘other’ category for the purpose of the analyses.

### **3.5 DATA MONITORING COMMITTEE AND INTERIM ANALYSES**

A Data Monitoring Committee (DMC) was appointed in line with standard CTU procedures. The responsibility of the group is to assess the data at each interim review, as the updates to the randomisation scheme occur in order to ensure that the process is working correctly and to review and monitor the accruing data to ensure the rights, safety, and wellbeing of the trial participants. They will make recommendations to the Trial Steering Committee (TSC) about how the trial is operating, any ethical or safety issues and any data being produced from other relevant studies that might impact the trial.

All DMC reports can be found on the PC-CTU restricted drive “K:\ID\ALABAMA\STATS\4. TSC and DMC\DMC”

No interim analysis for efficacy was planned for this study.

## 4 PRIMARY ANALYSIS

The primary objective is to determine whether the PAAP intervention is clinically effective in improving antibiotic prescribing.

### 4.1 PRIMARY OUTCOME

The primary outcome is penicillin prescribing, defined as the proportion of participants who receive prescriptions for a penicillin when attending for predefined conditions where a penicillin is the first-line recommended antibiotic up to 12 months post-randomisation. A binomial mixed-effects generalised linear model (MEGLM) with a logit link function will be fitted to the data with penicillin prescribing within 12 months of randomisation, as the dependent variable. The model will include randomised group, age, number of antibiotic prescriptions (as a continuous variable) up to the 24 months prior to randomisation (up to 12 months for those recruited to the nested pilot study), and the number of QOF registered diseases as fixed effects. These variables will come from the clinical database. GP practice will be included as a random effect. The adjusted relative risk between the randomised groups and the corresponding 95% confidence intervals will be obtained from the marginal adjusted relative risk (based on delta-method standard errors (Norton et al. 2013)) between the randomised groups and reported alongside the associated P-value.

### 4.2 HANDLING MISSING DATA

Missing data will be reported, with reasons where available. The mixed effects regression model assumes data is missing at random (MAR), however the mechanism of missing data will be explored. The baseline characteristics listed in section 3.2 (except those that were patient reported, and the ones from Sortition used in the randomisation) will be summarised for both randomised groups, split depending on if the primary outcome is available or missing. A logistic regression model will explore any association between each baseline characteristic and the availability of the primary outcome. Covariates found to be predictive of missingness ( $P<0.05$ ) will be included in the analysis model in a sensitivity analysis of the primary outcome (see section 6). If the primary outcome is available for all participants this will not be conducted.

Should any covariates (to be included in the model) have missing baseline data, the overall mean of the covariate at baseline will replace the missing values (Sullivan et al. 2018) to enable all randomised participants with outcome data to be included in the analysis.

### 4.3 HANDLING OUTLIERS

The primary outcome is a binary outcome collected from the notes reviews and the SystmOne database and hospital prescribing report, as such there is no expectation that there will be outliers.

### 4.4 MULTIPLE COMPARISONS AND MULTIPLICITY

This is a two-arm trial with one primary outcome which is clearly stated in the protocol. Thus, no adjustment for multiple comparisons is necessary. An effect will be interpreted as significant if the P-value is below 0.05.

## 5 SECONDARY ANALYSIS

### 5.1 BINARY OUTCOMES

The binary secondary outcomes:

- Treatment “response failure”,
- Hospital admission,
- Mortality rates,
- MRSA infection/colonisation,
- *Clostridioides difficile* infection,
- De-labelling at 3 months post randomisation (to be analysed in the as treated population),
- And de-labelling up to 12 months post randomisation (to be analysed in the as treated population)

will be analysed using a binomial mixed-effects generalised linear model with a logit link function. The models will include randomised group (as treated group for the de-labelling outcomes), age, number of antibiotic prescriptions in the 24 months prior to randomisation (12 months for those recruited to the nested pilot study), and the number of QOF registered diseases as fixed effects. GP practice will be included as a random effect. The adjusted relative risk between the randomised groups and the corresponding 95% confidence intervals will be obtained from the marginal adjusted relative risk between the randomised groups and reported alongside the associated P-value.

If it is possible that the de-labelling outcomes could unblind the report, the summary statistics will not be presented in the blinded report, only the treatment effects will. In this case, the summaries will only be presented in the unblinded report, once the blinded report is signed off. If there is insufficient data to compare the treatment groups, no formal analysis will be carried out and only summary statistics will be presented.

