### 1.4.2 SECONDARY OBJECTIVES

- 1) To determine whether the PAAP intervention is clinically effective in improving treatment response failure,
- 2) Effects of PAAP on symptom duration,
- 3) Effects of PAAP on total antibiotic prescribing,
- 4) Effects of PAAP on hospital admissions and length of hospital stays (safety outcomes),
- 5) Effects of PAAP on mortality rates (safety outcome),
- 6) Effects of PAAP on Meticillin-resistant *Staphylococcus aureus* (MRSA) infection/colonisation,
- 7) Effects of PAAP on *Clostridioides difficile* infection,

- 8) To explore patient and clinical views and experiences of penicillin allergy testing, test results, and future antibiotic use,
- 9) (Process evaluation) To explore patient and clinician experiences of trial procedures,
- 10) To measure the influences on clinician and patient behaviour change regarding prescribing and consuming penicillin following a negative test result,
- 11) Cost effectiveness for the PAAP intervention compared to usual care,
- 12) Effects of PAAP on de-labelling:
  - a) at 3 months post randomisation,
  - b) up to 12 months post randomisation.
- 13) Additional safety outcomes (exploratory outcome)
- 14) Effects of PAAP on all outcomes for follow up post 12 months.

N.B. Objectives 8, 9, 10, and 11 will be analysed as part of the qualitative, economic, and process evaluation and will be reported separately from the main statistical analysis report.

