### **3.3 DEFINITION OF POPULATION FOR ANALYSIS**

The primary analysis population will include all randomised patients in the treatment arm they were assigned to, regardless of treatment received. All data will be included in the analysis as far as possible, though there will inevitably be the problem of missing data due to withdrawal, loss to follow-up, or non-response to questionnaire items.

Participants withdrawn for post-randomisation ineligibility will be excluded from the analyses. Those randomised but who were not eligible at the PAAP clinic will not be included in the analysis population. Those who were eligible but decided not to go ahead with PAAP will be included in the analysis population.

The primary analysis will also be carried out on the “as treated” (AT) analysis population. All participants who were allocated to PAAP and had exposure to the test (i.e., they completed either the skin test or oral challenge test, or both), will be included in the as-treated PAAP arm. Those participants who were randomised to PAAP but did not have a test or who were randomised to usual care will be included in the usual care arm.

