### **6.1 AS TREATED (AT)**

Participants were analysed in their randomly assigned intervention arm for the primary analysis regardless of whether they received the intervention or not. A sensitivity analysis will be conducted analysing participants depending on whether they received the allocated intervention or not. The definition of the “as treated” (AT) analysis population is described in section 3.3.

The model used in the primary analysis (section 4.1) will be re-run on the AT group, with age, number of antibiotic prescriptions in the 24 months (12 months for those recruited to the nested pilot study) prior to randomisation, and the number of QOF registered diseases as fixed effects. GP practice will be included as a random effect. The adjusted relative risk between the AT groups and the corresponding 95% confidence intervals will be obtained from the model and reported alongside the associated P-value.

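### Both de-labelling outcomes are modelled only by as-treated group, yet Section 5.1 labels the result a relative risk between randomised groups

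*SAP*

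**What the plan says.** Section 1.4.2 sets objective 12 as "Effects of PAAP on de-labelling", at 3 months and up to 12 months. Sections 2.1.2.8 and 2.1.2.9 define the two outcomes over trial participants, not over those who were tested.

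Section 5.1 lists "De-labelling at 3 months post randomisation (to be analysed in the as treated population" among the binary outcomes, says the same of the 12-month outcome, and substitutes as-treated group for randomised group in the model. One reporting sentence then serves all seven binary outcomes: "The adjusted relative risk between the randomised groups and the corresponding 95% confidence intervals will be obtained from the marginal adjusted relative risk". It makes no exception for de-labelling.

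Section 3.3 defines the as-treated comparator: participants "randomised to PAAP but did not have a test or who were randomised to usual care will be included in the usual care arm". It also states: "Those randomised but who were not eligible at the PAAP clinic will not be included in the analysis population".

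Section 5.1 adds two conditions. If de-labelling could unblind the report, "the summary statistics will not be presented in the blinded report, only the treatment effects will" until sign-off. If data are insufficient, "no formal analysis will be carried out and only summary statistics will be presented".

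Section 6.1, on the as-treated analysis of the primary outcome, words its result differently: "The adjusted relative risk between the AT groups and the corresponding 95% confidence intervals will be obtained from the model".

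**The concern.** The section contradicts itself. A model whose only group term is as-treated group yields a contrast between tested and untested people. It cannot yield a contrast between randomised groups, and the text says it will.

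The contrast that is modelled also does not answer objective 12. PAAP is a pathway, and attending for testing is part of it. When someone allocated to PAAP is not tested, that is a result of the pathway. The as-treated rule takes that person out of the PAAP arm and adds them to usual care, so randomisation no longer protects the comparison. The rule also has no time limit: a participant first tested after day 90 counts as PAAP for the 3-month outcome. Section 6.4 expects delays of that length but deals with them for the primary outcome only.

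De-labelling is the step through which PAAP should change prescribing, so readers will use this estimate to interpret the primary result. As written, they would see a tested-versus-untested figure under a label that says randomised.

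**Working it through.** **Is a randomised-group estimate planned elsewhere?**

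- Sections 2.1.2.8, 2.1.2.9 and Appendix I only define the outcomes. Section 2.1.2.9 adds a count of relabelled participants by arm.
- Section 3.1 gives crude frequencies by randomised arm, with no adjusted estimate or confidence interval for the effect.
- Section 6 is limited to the primary outcome. Its stated exception points to a Section 6.6 that does not exist.
- Section 7 re-runs the primary analysis only. Section 8 covers hospital outcomes only.

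So none is planned. The data should exist, because Section 2.4 keeps PAAP participants who do not attend for testing in follow-up unless they withdraw consent.

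**Size.** The SAP states no power, uptake or rate for de-labelling, so there is no figure of its own to reproduce. Only the arm size is taken from it: 424 per group (Section 2.3). That figure does reproduce: 4% v 14% at 90% power, two-sided 5%, with continuity correction, needs 190 per arm; 190/0.9 = 211.1, rounded up to 212; 212/0.5 = 424.

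Assumed inputs:
- d = 0.90, the share of the tested who are de-labelled
- q = 0.20, the untested share of PAAP participants in the analysis population
- c, the share of usual care de-labelled
- e, the share of untested PAAP participants de-labelled

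Formulas, with N = 424:
- Randomised: (1−q)d + qe on N, against c on N.
- As treated: d on N(1−q) = 339, against (c + qe)/(1+q) on N(1+q) = 509.
- Crude 95% CI: exp(ln RR ± 1.96 √[(1−p1)/(n1p1) + (1−p0)/(n0p0)]).

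| c | e | Randomised | As treated |
|---|---|---|---|
| 1% | 1% | 72.2% v 1.0%, RR 72.2 (28.0 to 186.5) | 90.0% v 1.0%, RR 90.0 (37.9 to 213.8) |
| 1% | 10% | 74.0% v 1.0%, RR 74.0 (28.7 to 191.1) | 90.0% v 2.5%, RR 36.0 (20.9 to 62.0) |
| 5% | 5% | 73.0% v 5.0%, RR 14.6 | 90.0% v 5.0%, RR 18.0 |
| 5% | 10% | 74.0% v 5.0%, RR 14.8 | 90.0% v 5.8%, RR 15.4 |
| 5% | 20% | 76.0% v 5.0%, RR 15.2 | 90.0% v 7.5%, RR 12.0 |

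**Direction.** The two relative risks are equal when ((1−q)d + qe)/c = d(1+q)/(c + qe). This gives e = 0.0245 at c = 0.01 and e = 0.1135 at c = 0.05. Below that value the as-treated relative risk is the larger; above it, the smaller.

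**Absolute scale.** If the untested are de-labelled at the usual-care rate (e = c), the as-treated risk difference is d − c and the randomised one is (1−q)(d − c). The ratio is 1/(1−q): 1.11 at q = 0.10 and 1.25 at q = 0.20. The randomised PAAP percentage of 72% to 74% has a 95% CI of about 4 points either side (1.96 √(0.722 × 0.278/424) = 0.043), well short of 90%.

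**Sparse events.** At c = 1%, the randomised usual-care arm expects 424 × 0.01 = 4.2 events. The as-treated comparator expects 509 × 0.01 = 5.1, or 509 × 0.025 = 12.7 when e = 10%. The insufficient-data fallback could therefore apply, most easily to the randomised comparison.

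**The case against.** The as-treated choice is deliberate and disclosed: Section 5.1 states it in both outcome bullets and again in the model sentence. These are secondary outcomes, and the primary analysis stays by assigned arm. On this view the label is a drafting slip in a generic sentence and takes a few words to correct. The measure reported from the model is the relative risk, whose shifts lie mostly within sampling error. The clearer shifts, in the PAAP percentage and the risk difference, are not planned model outputs, and Section 3.1 would show the crude percentage by randomised arm anyway. A reversed direction needs untested PAAP participants to be de-labelled well above the usual-care rate, and nothing in the SAP shows that they would be. Suppression in the blinded report is conditional and temporary.

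Much of this stands. The choice is open, every rate is assumed, the relative-risk intervals overlap widely, and the reversal is a possibility only. Patients who previously tested negative but still carry a label are eligible (Section 2.2.1), so a route to de-labelling without a trial test exists. Randomisation should balance such patients across arms, however, so this does not show a higher rate among the untested. The missing Section 6.6 is probably a stale cross-reference.

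None of it supplies the missing estimate. Disclosure does not make a tested-versus-untested contrast an effect of PAAP, and the SAP gives no reason for treating de-labelling differently from its other modelled outcomes. Crude percentages by arm carry no adjusted effect or interval, and they may be withheld from the blinded report, leaving the mislabelled relative risk on its own until sign-off.

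**Conclusion.** The point holds and should be fixed. Three things follow from the text alone: the only model for either de-labelling outcome is by as-treated group; its result carries the wrong label; and objective 12 has no adjusted randomised-group estimate.

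The size rests on assumed rates. At 20% untested and 90% of the tested de-labelled, the PAAP figure differs by 16 to 18 points in the 1% usual-care cases (72% to 74% against 90%). The relative risk may be overstated or understated, depending on how often untested PAAP participants are de-labelled. With high uptake the gap is small: at 5% untested, and with the untested at the usual-care rate, the risk difference is inflated by about 5% (1/0.95). The conclusion that PAAP increases de-labelling would probably survive, and the primary outcome is unaffected.

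**What to change.** In Section 5.1, make the stated mixed model with randomised group, on the Section 3.3 primary analysis population, the main analysis of both de-labelling outcomes. Keep the as-treated model as supportive and describe its relative risk as being between the as-treated groups, in line with Section 6.1. If the insufficient-data fallback applies, present the summaries by randomised arm. State in the report that participants found ineligible at the clinic are outside this population, so even the randomised-group estimate does not describe everyone offered the pathway. Correct or delete the reference to Section 6.6.

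The cost is SAP wording and one rerun of an already specified model per outcome, with no new data. The de-labelling percentage presented for PAAP alongside the main estimate would probably be less favourable than the as-treated one.

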## 2.3 SAMPLE SIZE

The primary outcome was initially treatment response failure defined as the percentage of re-prescription of an alternative antimicrobial within 28 days of an index prescription. A total sample size between 1592 and 2090 participants provided 80-90% power to detect a clinically important absolute difference of 7.9% in re-prescription rate at one year between groups (i.e. reducing from 19.8% in the control group to 11.9% in the PAAP group) at 5% level of significance (2-sided). The sample size had been adjusted assuming 50% of participants will require at least one prescription within 1 year from randomisation and allowing for 10% dropout. Participants are classed as enrolled at the point of randomisation.

The primary outcome was then changed to 'effects of PAAP on penicillin prescribing', defined as 'The proportion of participants who receive prescriptions for a penicillin attending for predefined conditions where a penicillin is the first-line recommended antibiotic (see Appendix II) during the course of routine primary care up to 12 months post randomisation. A total sample of 848 (i.e. 424 per group) was required to provide 90% power to detect an increase in the proportion of penicillin prescription from 4% (Usual Care) to 14% (PAAP) over the year after randomisation at 5% level of significance (2-sided) and 10% attrition. The sample size has been adjusted assuming 50% of participants will require at least one prescription within 1 year from randomisation. At 80% power, the sample size required was 656 (i.e. 328 per group). The table below also provides the sample size required if not all participants have reached 12 months follow-up.

Power	% Difference	Total sample size (all reached 12 months FU)	Total sample size (80% reached 12 months FU)	Total sample size (90% reached 12 months FU)
80%	10%	656	820	729
	15%	372	465	413
90%	10%	848	1060	942
	15%	472	590	524

Results from our recent analysis, using data extracted from the SystmOne database, suggested that there were an average of 110 patients per average practice size of 6000 who fulfilled our inclusion criteria.

- 1) Adults (over 18 years),
- 2) Penicillin allergy in electronic health records,
- 3) And in receipt of a penicillin, cephalosporin, tetracycline, quinolone, or macrolide class antimicrobial in the previous 24 months.

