## **3 ANALYSIS – GENERAL CONSIDERATIONS**

### **3.1 DESCRIPTIVE STATISTICS**

Frequencies (with percentages) for binary and categorical variables, and means (with standard deviations), or medians (with lower and upper quartiles), and the range (minimum and maximum values) for continuous variables will be presented by randomised arm.

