### 5.2 CONTINUOUS OUTCOMES

The continuous secondary outcomes:

- Duration of symptoms rated ‘moderately bad’ or worse,
- Number of days of antibiotic use (total and split by penicillin and non-penicillin, and antibiotic class)
- Defined daily dose (DDD) (total and split by penicillin and non-penicillin and antibiotic class),
- And length of hospital stays,

will be analysed using a linear mixed effects regression model. The models will include randomised group, age, number of antibiotic prescriptions in the 24 months prior to randomisation (12 months for those recruited to the nested pilot study), and the number of QOF registered diseases as fixed effects. GP practice will be included as a random effect. The adjusted mean difference between the randomised groups with 95% confidence intervals and P-values will be reported.

The proposed analyses assumes that these secondary outcomes satisfy the assumptions of the linear mixed effects regression model. Histograms of the distribution of each outcome split by randomised group, and post estimate plots of the residuals will be presented. If the post estimate plots show evidence that the assumptions of the linear mixed effects regression model have been violated, transformation of the data will be attempted. If there is still evidence that the assumptions have been violated a quantile regression will be implemented. The quantile regression will include randomised group, age, number of antibiotic prescriptions in the 24 months prior to randomisation (12 months for those recruited to the nested pilot study), number of QOF registered diseases, and GP practice as covariates. The adjusted median difference between the randomised groups with

95% confidence intervals, and P-values will be reported. If the quantile regression does not converge an unadjusted quantile regression will be attempted; if the model still does not converge a non-parametric approach such as a Mann-Whitney U test will be adopted.

Defined daily dose (DDD) split by class, is expected to be small for some classes in each randomised arm. If it is judged to be too small this will only be presented descriptively.

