### **5.3 COUNT OUTCOMES**

The count secondary outcomes:

- Number of antibiotic prescriptions (total and split by penicillin and non-penicillin, and antibiotic class),
- Number of hospital admissions (within 56 days of primary event onset), and 12 months

will be analysed using a Poisson mixed effects regression model. The models will include randomised group, age, number of antibiotic prescriptions in the 24 months prior to randomisation (12 months for those recruited to the nested pilot study), and the number of QOF registered diseases as fixed effects. GP practice will be included as a random effect. The adjusted incidence rate ratio between the randomised groups with 95% confidence intervals, and P-values will be obtained from the model.

If there are excess zeros and/or over dispersion in the data, the Poisson model will be run with robust standard errors. If the model fails to converge, a zero-inflated Poisson model and/or a negative binomial model will be considered to analyse these outcomes.

Number of antibiotics split by class is expected to be small in some antibiotic classes in each randomised arm. If it is judged to be too small this will only be presented descriptively.

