If the list and description of the adverse events could potentially unblind the report, this will not be presented in the blinded version of the report, only the summary statistics will be provided. In this case the detailed list of adverse events will only be presented in the unblinded report, which will only be prepared when the blinded report has been signed off.

A serious adverse event (SAE) is any untoward medical occurrence that:

- Results in death,
- Is life-threatening,
- Requires inpatient hospitalisation or prolongation of existing hospitalisation,
- Results in persistent or significant disability/incapacity,
- Or consists of a congenital anomaly or birth defect.

Other important medical events' may also be considered serious if they jeopardise the participant or require an intervention to prevent one of the above consequences.

- Anaphylaxis to an antibiotic will be considered an SAE as part of the ALABAMA trial.

NOTE: The term "life-threatening" in the definition of "serious" refers to an event in which the participant was at risk of death at the time of the event; it does not refer to an event which hypothetically might have caused death if it were more severe.

The number and percentage of participants experiencing at least one SAE will be reported by the intervention they received (rather than the intervention they were randomised to receive) and will be analysed using a Fisher's Exact test if possible. The total number of SAEs per AT group will be reported for each serious adverse event. The total number of SAEs per AT group will also be reported.

Any SAEs identified during the ALABAMA trial need to be assessed for their relatedness to:

1. Penicillin Allergy Assessment (PAA)
2. An antibiotic prescription\* for any of the pre-defined infections listed in Appendix G of the protocol and Appendix II of this document.

\*Because patients may have more than one antibiotic prescription during the ALABAMA trial, the relatedness of SAEs was assessed in relation to their most recent antibiotic prescription for any pre-defined infections.

SAE description, start date of SAE, stop date of SAE, severity of the event, reason the event was classified as serious, event related to intervention, was the event unexpected, outcome of the SAE, allocated intervention group, and received intervention, will be reported for each serious adverse event.

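### Section 5.1 names no sparse-data method for binary outcomes, so deaths, MRSA and C. difficile could be reported with no bound on the difference between arms

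*SAP*

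**What the plan says.** Section 5.1 states that the binary secondary outcomes, including mortality, MRSA and C. difficile, "will be analysed using a binomial mixed-effects generalised linear model with a logit link function". Age, prior antibiotic prescriptions and number of QOF diseases are fixed effects and practice is a random effect. The result is a marginal adjusted relative risk with a 95% interval and P-value. The section ends: "If there is insufficient data to compare the treatment groups, no formal analysis will be carried out and only summary statistics will be presented". It does not define insufficient data or name a simpler model. The two sentences just before concern only whether de-labelling results could unblind the report.

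Section 3.1 says what summary statistics means here: "Frequencies (with percentages) for binary and categorical variables". Section 1.4.2 lists "Effects of PAAP on mortality rates (safety outcome").

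Other sections do step down:
- Section 5.2 (continuous outcomes) goes through transformation and quantile regression, and then "if the model still does not converge a non-parametric approach such as a Mann-Whitney U test will be adopted".
- Section 5.3 (count outcomes) uses robust standard errors for excess zeros or overdispersion, and then "If the model fails to converge, a zero-inflated Poisson model and/or a negative binomial model will be considered to analyse these outcomes".
- Section 9 says that participants with at least one SAE, grouped by intervention received, "will be analysed using a Fisher's Exact test if possible".

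**The concern.** For rare binary outcomes the plan has nothing between a full mixed model and plain description. When one arm has no events, the maximum-likelihood treatment coefficient does not exist, however many events the other arm has. No relative risk with an interval can then be reported from that model. The same holds when neither arm has an event.

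What would be lost is a statement of how large a difference the data exclude. That is the useful result for a safety outcome with few events, and it can be had even when no one in either arm has the event. The point at which formal analysis is abandoned is also left to judgement once the data are in.

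**Working it through.** **Arm size.** Section 2.3 says "A total sample of 848 (i.e. 424 per group) was required to provide 90% power", for 4% v 14%, two-sided 5%, 50% of participants contributing and 10% attrition. To reproduce it:
- Uncorrected n per arm = [1.960·√(2·0.09·0.91) + 1.282·√(0.04·0.96 + 0.14·0.86)]² / 0.10² = 170.0.
- With continuity correction, n' = (n/4)·[1 + √(1 + 4/(n·0.10))]² = 189.5, so 190.
- 190/0.5 = 380; 380/0.9 = 422.2, so 423 per arm and 846 in total. The SAP states 848, so the figure reproduces to within rounding.

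I assume that 10% attrition applies to these outcomes too: 424 × 0.9 = 381.6, taken as 382 per arm.

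**The model with a zero cell.** I fitted a plain logistic model by maximum likelihood to 0 v 7 events at 424 per arm. The arm coefficient was -7.5 (SE 9.6) after 10 iterations, -17.5 (SE 1420) after 20, and about -34 (SE about 3 million) after 40. It diverges. Adding covariates and a practice effect does not cure this.

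**What an unadjusted comparison gives at 382 per arm.** The Newcombe interval for d = p1 - p2 combines the Wilson limits (l, u) of each arm:
- lower = d - √[(p1 - l1)² + (u2 - p2)²]
- upper = d + √[(u1 - p1)² + (p2 - l2)²]

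For an arm with no events, l = 0 and u = 3.84/(382 + 3.84) = 1.00%. For 6/382 = 1.57%, the Wilson limits are 0.72% and 3.38%. The lower limit for 6 v 0 is therefore 1.57 - √(0.85² + 1.00²) = 0.26, and the upper is 1.57 + (3.38 - 1.57) = 3.38.

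| Events | Difference (points) | 95% interval | Fisher P |
|---|---|---|---|
| 0 v 0 | 0 | -1.0 to 1.0 | 1 |
| 4 v 0 | 1.0 | -0.1 to 2.7 | 0.12 |
| 5 v 0 | 1.3 | 0.06 to 3.0 | 0.06 |
| 6 v 0 | 1.6 | 0.3 to 3.4 | 0.03 |
| 8 v 0 | 2.1 | 0.7 to 4.1 | 0.008 |

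At 328 or 424 per arm, Fisher's test for 6 v 0 still gives P=0.03.

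**How likely a zero cell is.** The SAP gives no event rates, so I assume a common 12-month risk r. With q = (1 - r)^382, the chance that exactly one arm has no events is 2q(1 - q). The last column is 2q·P(6 or more events in the other arm).

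| r | q | Exactly one arm zero | Of which 0 v 6 or more |
|---|---|---|---|
| 0.1% | 0.682 | 43% | 0.0004% |
| 0.2% | 0.465 | 50% | 0.01% |
| 0.5% | 0.147 | 25% | 0.4% |
| 1% | 0.021 | 4% | 0.8% |

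If the arms truly differ, 0 v 6 or more becomes likelier: 13% for 0.1% v 1% (0.682 × 0.187) and 36% for 0.2% v 2% (0.465 × 0.776).

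**The case against.** A reader might infer that Section 5.1 requires a split such as 6 v 0 or 8 v 0 to be reported descriptively. It does not. It mentions neither a zero cell, nor non-convergence, nor a minimum number of events, and an analyst could judge such data sufficient. By its position the sentence may also cover only de-labelling. Both points stand, and they limit the claim to what could happen. They do not remove the gap: on the narrow reading, mortality, MRSA and C. difficile have no fallback at all.

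A reader might also infer that the undefined trigger lets the analyst choose in favour of one arm. Section 2.4 keeps the trial statistician blinded during the final analysis, and Sections 5.1 and 9 hold back potentially unblinding detail until the blinded report is signed off. The documents do not support that charge.

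The loss of information is modest. Counts and percentages by arm would be published, so others could compute an interval. Deaths also count as SAEs in Section 9, which reports SAEs by group and applies Fisher's test. But that test pools every kind of SAE and groups participants by intervention received. It does not compare deaths between randomised arms, and it does not address MRSA or C. difficile as outcomes.

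Finally, describing very rare events without a test is accepted practice, and Sections 5.2 and 5.3 do so for small antibiotic classes. For the test this is fair, since up to 5 v 0 Fisher's P exceeds 0.05. It is a weaker argument against giving an interval.

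**Conclusion.** The point holds as a gap in the specification of secondary and safety outcomes. With no events in an arm, the only named model yields no treatment estimate. The only sparse-data rule is undefined in trigger and scope, and it ends in description. Mortality, MRSA and C. difficile could therefore be reported with no bound on the between-arm difference, although at about 382 per arm even 0 v 0 limits it to within 1.0 point either way.

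This rests on two assumptions: 10% attrition from 424 per arm, and common 12-month risks of 0.1% to 1%. A zero in exactly one arm is a realistic prospect at 0.5% or below (25% to 50%) and unlikely at 1% (4%). Under a common risk, 0 v 6 or more has less than a 1% chance, so the main gain is the interval and not the P-value. No primary result is affected.

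**What to change.** State in Section 5.1 that the sparse-data rule applies to all binary secondary outcomes, and replace the provision for no formal analysis with:

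*If either arm has no events or the mixed model does not converge, the counts by randomised arm (as-treated group for de-labelling) will be reported with the unadjusted risk difference and its 95% score (Newcombe) interval as the main result; Fisher's exact P-value may be added as supporting information.*

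Naming the interval as the main result matters because the two methods can disagree: at 5 v 0 the interval just excludes zero (0.06 to 3.0) while Fisher's P is 0.06.

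The cost is one sentence and a few lines of code. The downside is that the comparison is not adjusted for the minimisation factors, in a situation where the adjusted model could not be estimated.
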